7.5.5 Individual Subject Discontinuation

During this study, it is anticipated that some subjects may permanently discontinue study medication (vadadustat or darbepoetin alfa) for any of the following reasons:

- Unacceptable toxicity or drug intolerance
- Investigator discretion
- Subject withdrawal of consent
- Subject becomes pregnant
- Subject receives kidney transplant
- Lack of efficacy
- Other reasons.

Lack of efficacy is defined as inadequate response to darbepoetin alfa or vadadustat in the Investigator's opinion.

Subjects who undergo a solid organ (including kidney), hematopoietic stem cell, or bone marrow transplantation will have their study medication (vadadustat or darbepoetin alfa) permanently discontinued.

See [Section 9.4, Study Medication Stopping Rules](#) for additional details on the management of subjects with ALT and AST abnormalities.

It is important to continue to follow subjects that permanently discontinue study medication. Please see [Section 7.5.5.1, Temporary Interruption of Study Medication](#) and [Section 7.5.5.2, Permanent Discontinuation of Study Medication](#), and [Appendix A: Schedule of Activities](#).

Receipt of rescue therapy is not a reason for permanent study medication discontinuation. While receiving ESA rescue, subjects must temporarily discontinue study medication (vadadustat or darbepoetin alfa), but should resume study medication once rescue therapy has ended, as detailed in [Section 8.4.7, Rescue Therapy](#).

As part of the informed consent process, only subjects who fully understand and agree to full participation and long-term follow-up should be consented to participate.

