7.5.5.1 Temporary Interruption of Study Medication

Subjects who temporarily interrupt study medication (vadadustat or darbepoetin alfa) treatment after the first dose and prior to completion of the study will continue with study visits and assessments. **Unless contraindicated, treatment should be resumed wherever possible and routinely considered at every visit following study medication discontinuation.** If a subject does not return for a scheduled visit, every effort should be made to contact the subject. If a subject's

study medication has been temporarily interrupted for more than 60 days, the Investigator should contact the Medical Monitor before resuming study medication.

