9.4 Study Medication Stopping Rules

Study medication must be permanently discontinued if a subject meets one of the criteria in Table 2 below

Table 2. Study Medication Stopping Rules

ALT or AST >3x ULN and total bilirubin >2x ULN	Permanently Discontinue Treatment
ALT or AST >3x ULN and INR >1.5	Permanently Discontinue Treatment
ALT or AST >8x ULN	Permanently Discontinue Treatment
ALT or AST remains >5x ULN over 2 weeks*	Permanently Discontinue Treatment

ALT or AST >3x ULN with symptoms including e.g., fatigue, nausea, vomiting, right upper quadrant pain, fever, rash or eosinophilia	Permanently Discontinue Treatment
--	-----------------------------------

* Re-challenge generally should be avoided with ALT or AST >5x ULN unless there are no other good therapeutic options.

ALT: alanine transferase; AST: asparagine transferase; INR: international normalized ratio; ULN: upper limit of normal

See Section 10.1.1, Adverse Events for reporting requirements related to a subject being permanently discontinued based on meeting the laboratory abnormalities list above in [Table 2](#).

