Procedures – Diagnostic and therapeutic non-invasive and invasive procedures, such as surgery, should not be reported as AEs. However, the medical condition for which the procedure was performed should be reported if it meets the definition of an AE. For example, an acute appendicitis that begins during the AE reporting period should be reported as the AE and the resulting appendectomy noted under ‘Comments’.

Pre-planned therapeutic procedures not associated with a new medical condition or worsening pre-existing condition should not be reported as AEs.

Pre-existing Conditions – In this study, a pre-existing condition (ie, a disorder present before the AE reporting period started and noted on the pretreatment medical history/physical examination form) should not be reported as an AE unless the condition worsens, or episodes increase in frequency during the AE reporting period.

Abnormal Test Findings – All laboratory test results will be reviewed by the Investigator. The Investigator will utilize his/her judgment in determining if out of range laboratory values are clinically significant and will denote this using the abbreviation “CS” on the laboratory report for source documentation. Laboratory tests that are labeled as clinically significant should be reported as AEs, either separately or as part of a description of a symptomatic AE. If there are significant changes in a laboratory report from a previous visit that are determined to be clinically significant, these should also be reported as AEs. Any abnormal laboratory value which requires treatment or further diagnostic testing and/or results in discontinuation from study should be reported as an AE. An expected laboratory abnormality from a condition that is part of the medical history is not considered clinically significant for the purposes of the study unless it represents a worsening of the condition.

Abnormalities in ALT, AST and Total Bilirubin – Abnormalities in ALT, AST and total bilirubin should be reported to the Sponsor’s Medical Monitor or CRO designee within 24 hours of awareness as an SAE with ‘other medically important event’ criterion selected, if the following conditions are met:

- New elevation in ALT or AST >3 times ULN, with or without an elevation of total serum bilirubin >2 times ULN, AND

If new elevations in ALT or AST >3 times ULN, **without** an elevation of total serum bilirubin >2 times ULN are identified, the following steps are to be taken:

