- Temporary discontinuation of study medication.
- Repeat testing of ALT, AST, ALP, and total bilirubin, should be completed within 48 to 72 hours to confirm the abnormalities and to determine trend.
- Study medication should not be resumed until monitoring indicates abnormalities have resolved, are stable, or are not rapidly increasing.

Details on the management of subjects with other ALT and AST abnormalities are further described in [Section 9.4, Study Medication Stopping Rules](#).

Worsening of Anemia – In this study, it is possible that some subjects may experience a worsening of anemia. As the primary endpoint of this study assesses Hb response, worsening of anemia is captured as part of this efficacy parameter. Worsening of anemia should not be considered an AE unless the worsening of anemia is associated with a cause *other than* the subject's CKD.

Transplantation – During this long-term study, it is anticipated that some subjects may receive a kidney transplant. These events will not be recorded as AEs. Subjects will discontinue study medication for receipt of a kidney, other solid organ, hematopoietic stem cell or bone marrow transplant and should continue with the Schedule of Activities and safety assessments as described in [Section 7.5.5.2, Permanent Discontinuation of Study Medication](#).

Malignancy – During this long-term study, some subjects may develop a newly diagnosed malignancy or a recurrence of a malignancy. At the discretion of the Investigator, these subjects may continue study medication (vadadustat or darbepoetin alfa). For reporting of adverse events of malignancy, see Section 10.1.2 Serious Adverse Events.

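### For ALT/AST above 5x and up to 8x ULN, the Section 10.1.1 restart condition can be met before the mandatory two-week stop in Section 9.4 can be decided, and no liver test is dated for that decision

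*Protocol*

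**What the plan says.** All references are to the current protocol text (Amendment 6).

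- **Section 9.4, Table 2.** Permanent discontinuation is mandatory if any listed criterion is met. One criterion is "ALT or AST remains >5x ULN over 2 weeks". The others are ALT/AST above 8x ULN, or above 3x ULN together with bilirubin above 2x ULN, INR above 1.5, symptoms or eosinophilia.
- **Section 9.4, footnote to the two-week row (repeated in the synopsis).** "Re-challenge generally should be avoided with ALT or AST >5x ULN unless there are no other good therapeutic options".
- **Section 10.1.1, ALT, AST and total bilirubin.** For new ALT/AST above 3x ULN without bilirubin above 2x ULN, study medication is temporarily stopped. A repeat panel "should be completed within 48 to 72 hours to confirm the abnormalities and to determine trend". Then: "Study medication should not be resumed until monitoring indicates abnormalities have resolved, are stable, or are not rapidly increasing". The paragraph closes with a pointer to Section 9.4: "Details on the management of subjects with other ALT and AST abnormalities are further described in".
- **Section 7.5.5.** It refers the reader to Section 9.4 "for additional details on the management of subjects with ALT and AST abnormalities".
- **Section 7.5.5.1.** For interruptions in general: "Unless contraindicated, treatment should be resumed wherever possible and routinely considered at every visit". It sets no minimum interruption. Contact with the Medical Monitor before restarting is asked for only after more than 60 days.
- **Section 9.2.2.** Liver panels after Baseline are at Weeks 4, 8, 12, 16, 20, 24, 28, 36, 44, 52, 64, 76, 88, 104, 116, 128, 140, 156, 168, 180, 192 and 208, and at end of treatment.

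**The concern.** The two-week rule can only be applied to someone whose values are followed for two weeks, and it ends in a permanent stop. Section 10.1.1 governs the same subject from the day of the finding, yet its restart condition is about trend only. Stable is enough, whatever the level. A subject could therefore satisfy the restart condition within days and, on the same values, be due for permanent discontinuation a week and a half later.

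What is at stake is re-exposure of a subject with a marked, unexplained transaminase rise while a mandatory liver stop is still undecided. Appendix E says Amendment 6 introduced these rules because of FDA guidance on possible drug-induced liver injury. That amendment removed the raised-bilirubin case from the temporary-stop path in Section 10.1.1 because it had become a permanent-stop criterion. It made no matching adjustment for the two-week criterion. Two investigators, one working from Section 10.1.1 and one reading it together with Section 9.4, could handle the same subject differently.

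**Working it through.** The plan states no figure on this point to reproduce. The check compares the sections and then counts days.

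**1. Who is affected.** Above 8x ULN, Section 9.4 stops drug at once. Between 3x and 5x ULN the two-week criterion does not apply. With bilirubin above 2x, INR above 1.5, symptoms or eosinophilia, Section 9.4 again stops drug at once. What is left is ALT/AST above 5x and up to 8x ULN with none of those features.

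**2. Is the restart condition met early?** Take a value of 6x ULN on Day 0 and 6x ULN at the required repeat (illustrative values inside the band). The repeat falls at 48 to 72 hours, that is Day 2 to Day 3. The abnormality is stable, and the three alternatives in the sentence are joined by *or*, so the condition is met.

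**3. Interval before the two-week criterion can be decided**, counting from the first value above 5x ULN:
- from a Day 3 repeat: 14 − 3 = 11 days
- from a Day 2 repeat: 14 − 2 = 12 days

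**4. Does any required test fall in or near that interval?** The 22 dated post-Baseline panels in Section 9.2.2 form 21 consecutive pairs:

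| Nominal gap | Pairs |
|---|---|
| 28 days | 6 |
| 56 days | 3 |
| 84 days | 9 |
| 112 days | 3 |

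6 + 3 + 9 + 3 = 21. Baseline to Week 4 is also 28 days. Visit windows (Section 9) are ±3 days to Week 12, ±5 days to Week 52 and ±10 days after. The tightest case is a four-week gap between two visits with ±5-day windows: 28 − 5 − 5 = 18 days, still more than 14. So no scheduled liver test falls within 14 days of another, even at the edge of the windows. For a finding at Week 4, the Week 6 visit falls nominally on Day 14, but Section 9.3.5 draws no liver panel there. The end-of-treatment panel has no fixed week and is not counted. An elevation found at an unscheduled visit could by chance precede a scheduled panel by about two weeks.

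**5. Does any other text close the gap?**

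| Text | Effect on restart above 5x ULN | Sets a retest date? |
|---|---|---|
| 9.4 footnote | Discourages it, with an exception; not cited in 10.1.1 | No |
| 10.1.1 pointer to 9.4 | Covers other abnormalities; does not make restart wait | No |
| 7.5.5 pointer to 9.4 | Sends the reader to the table and footnote | No |
| 7.5.5.1 | Favors restart unless contraindicated | No |
| 10.3.3 and 10.3.7 | SAE monitoring and follow-up until resolved or stable | No |
| 9.3.11 | Permits unscheduled tests; liver panel not in the required minimum | No |

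**The case against.** The strongest reply is that the sections can be read together without conflict. The restart sentence in Section 10.1.1 is a necessary condition, not an instruction to restart. Section 9.4 is mandatory and nothing overrides it. Section 7.5.5 sends ALT/AST abnormalities there, and Section 7.5.5.1 allows for contraindications. The footnote addresses exactly this act at exactly this level. Its exception should rarely apply, since Section 8.5.2 allows other ESAs when study medication is interrupted and Section 7.5.5.2 returns subjects to standard of care after a permanent stop. A persistent value above 5x can also be read as one of the other abnormalities that Section 10.1.1 refers to Section 9.4.

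Much of this stands. A reader might infer that Section 10.1.1 contradicts Section 9.4 or tells sites to restart; the text does neither. A careful investigator reading everything would probably wait and retest.

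A reader might also infer from the visit schedule that a subject could go untested for weeks or months. The documents do not support that as a realistic outcome. Section 10.1.1 asks for an SAE report within 24 hours and ties restart to monitoring, Section 10.3.3 calls for careful observation until the event resolves or stabilizes, and Section 9.3.11 allows unscheduled tests. The scheduled visits are routine surveillance, not event follow-up.

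What survives is narrower. The footnote is advisory and is not cited where the restart condition is stated. SAE follow-up may end once the value is merely stable. No provision dates the test on which a mandatory stop depends.

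**Conclusion.** The point holds for a narrow group: new ALT/AST above 5x and up to 8x ULN with no other Section 9.4 criterion. For them the restart condition can be met 11 to 12 days before the two-week criterion can be decided, the only specific brake is advisory, and no liver test near two weeks is required.

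The interval assumes that the two weeks run from the first value above 5x ULN and are judged at Day 14. If the criterion means longer than two weeks, the undecided interval is longer. The protocol does not say how many subjects would be affected, and the visit-pair counts above are not subject counts. Efficacy analysis and sample size are untouched. This is a low-cost improvement to patient safety, not a liver rule that fails.

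**What to change.** Change Section 10.1.1 only:

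- **(a) Restart.** State that resumption is subject to Section 9.4, and that study medication is not resumed while ALT or AST remains above 5x ULN until the two-week criterion has been assessed. Say explicitly that the footnote's re-challenge exception does not apply during that interval, so the hold and the footnote do not conflict.
- **(b) Dated test.** If the 48 to 72 hour repeat is still above 5x ULN, require a further liver panel about 14 days after the first value above 5x ULN.

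Section 7.5.5.1 needs no change, because Section 7.5.5 already refers to Section 9.4. The cost is a few lines of text, one extra blood panel and a somewhat longer interruption in few subjects.

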10 ADVERSE EVENTS

10.1 Definitions

10.1.1 Adverse Events

For the purposes of this study, an AE is any untoward medical occurrence (including a clinically significant abnormal laboratory finding) that occurs in the protocol-specified AE reporting period; the event does not necessarily have a causal relationship with that treatment or usage.

An AE includes medical conditions, signs, and symptoms not previously observed in the subject that emerge during the protocol-specified AE reporting period, including signs or symptoms associated with pre-existing underlying conditions that were not present prior to the AE reporting period.

Adverse events therefore include the following:

- All AEs, whether suspected to be causally related to study medication or otherwise.
- All AEs secondary to any medication overdose, medication error, abuse, withdrawal, sensitivity, or toxicity.
- Illnesses apparently unrelated to study medication, including the worsening of a pre-existing illness (see paragraph below on Pre-existing Conditions).
- Injury or accidents. Note that if a medical condition is known to have caused the injury or accident (eg, a fall secondary to dizziness), the medical condition (dizziness) and the accident (fall) should be reported as 2 separate AEs.
- Abnormalities in physiological testing or physical examination findings that require clinical intervention or further investigation (beyond ordering a repeat [confirmatory] test).
- Laboratory abnormalities that require clinical intervention or further investigation (beyond ordering a repeat [confirmatory] test) unless they are associated with an already reported clinical event. Laboratory abnormalities associated with a clinical event reported as an AE (eg, elevated liver enzymes in a subject with jaundice) should be described under 'Comments' on the report of the clinical event rather than reported as separate AEs.

The following guidelines are to be used when reporting AEs for this study:

Medical Diagnoses – Whenever possible, a medical diagnosis term should be used to report AEs instead of signs and symptoms due to a common etiology, as determined by qualified medical study staff. For example, pneumonia should be the reported AE term, instead of fever, dyspnea, etc., when the diagnosis has been established. Signs and symptoms should be reported as event terms only when the medical diagnosis remains unknown and revised to a medical diagnosis term once it has been established.

Procedures – Diagnostic and therapeutic non-invasive and invasive procedures, such as surgery, should not be reported as AEs. However, the medical condition for which the procedure was performed should be reported if it meets the definition of an AE. For example, an acute appendicitis that begins during the AE reporting period should be reported as the AE and the resulting appendectomy noted under ‘Comments’.

Pre-planned therapeutic procedures not associated with a new medical condition or worsening pre-existing condition should not be reported as AEs.

Pre-existing Conditions – In this study, a pre-existing condition (ie, a disorder present before the AE reporting period started and noted on the pretreatment medical history/physical examination form) should not be reported as an AE unless the condition worsens, or episodes increase in frequency during the AE reporting period.

Abnormal Test Findings – All laboratory test results will be reviewed by the Investigator. The Investigator will utilize his/her judgment in determining if out of range laboratory values are clinically significant and will denote this using the abbreviation “CS” on the laboratory report for source documentation. Laboratory tests that are labeled as clinically significant should be reported as AEs, either separately or as part of a description of a symptomatic AE. If there are significant changes in a laboratory report from a previous visit that are determined to be clinically significant, these should also be reported as AEs. Any abnormal laboratory value which requires treatment or further diagnostic testing and/or results in discontinuation from study should be reported as an AE. An expected laboratory abnormality from a condition that is part of the medical history is not considered clinically significant for the purposes of the study unless it represents a worsening of the condition.

Abnormalities in ALT, AST and Total Bilirubin – Abnormalities in ALT, AST and total bilirubin should be reported to the Sponsor’s Medical Monitor or CRO designee within 24 hours of awareness as an SAE with ‘other medically important event’ criterion selected, if the following conditions are met:

- New elevation in ALT or AST >3 times ULN, with or without an elevation of total serum bilirubin >2 times ULN, AND

If new elevations in ALT or AST >3 times ULN, **without** an elevation of total serum bilirubin >2 times ULN are identified, the following steps are to be taken:

- Temporary discontinuation of study medication.
- Repeat testing of ALT, AST, ALP, and total bilirubin, should be completed within 48 to 72 hours to confirm the abnormalities and to determine trend.
- Study medication should not be resumed until monitoring indicates abnormalities have resolved, are stable, or are not rapidly increasing.

Details on the management of subjects with other ALT and AST abnormalities are further described in [Section 9.4, Study Medication Stopping Rules](#).

Worsening of Anemia – In this study, it is possible that some subjects may experience a worsening of anemia. As the primary endpoint of this study assesses Hb response, worsening of anemia is captured as part of this efficacy parameter. Worsening of anemia should not be considered an AE unless the worsening of anemia is associated with a cause *other than* the subject's CKD.

Transplantation – During this long-term study, it is anticipated that some subjects may receive a kidney transplant. These events will not be recorded as AEs. Subjects will discontinue study medication for receipt of a kidney, other solid organ, hematopoietic stem cell or bone marrow transplant and should continue with the Schedule of Activities and safety assessments as described in [Section 7.5.5.2, Permanent Discontinuation of Study Medication](#).

Malignancy – During this long-term study, some subjects may develop a newly diagnosed malignancy or a recurrence of a malignancy. At the discretion of the Investigator, these subjects may continue study medication (vadadustat or darbepoetin alfa). For reporting of adverse events of malignancy, see Section 10.1.2 Serious Adverse Events.

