
Phlebotomy	If a subject's Hb exceeds 14.0 g/dL or the rate of rise of Hb raises concern to the Investigator, the subject may be phlebotomized based on the Investigator's clinical judgment. The method of phlebotomy will be in accordance with the investigative site's standard clinical practice.
Study Medication Stopping Rules	
Study medication must be permanently discontinued if a subject meets one of the criteria.
 
• ALT or AST >3x Upper Limit of Normal (ULN) and total bilirubin >2x ULN• ALT or AST >3x ULN and INR >1.5• ALT or AST >8x ULN• ALT or AST remains >5x ULN over 2 weeks*• ALT or AST >3x ULN with symptoms (e.g., fatigue, nausea, vomiting, right upper quadrant pain, fever, rash) or eosinophilia 
*Re-challenge generally should be avoided with ALT or AST >5x ULN unless there are no other good therapeutic options.

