9.2.2 Laboratory Evaluations

Samples for laboratory assays will be sent to a central laboratory for analysis. Detailed instructions for the collection, processing, and shipment of laboratory samples will be provided by the Sponsor and the central laboratory. If blood is collected on a hemodialysis day, blood draws should be done prior to dialysis, if applicable. The Investigator is responsible for reviewing laboratory results for clinical significance.

The following laboratory evaluations will be conducted during the course of the study:

- **Pregnancy Test:** A serum pregnancy test will be performed at SV2 for females of childbearing potential. Additional serum or local urine (if possible) pregnancy tests may be conducted throughout the study in sufficient number, as determined by the

Investigator or required by local regulations, to establish the absence of pregnancy during the study. The SV2 results must be available and must be negative before the subject takes the first dose of study medication.

- Complete Blood Count (CBC): A CBC with differential will be performed at Baseline and twice annually at Weeks 28, 52, 76, 104, 128, 156, 180, 208. At all other noted visits in [Appendix A: Schedule of Activities](#), including SV1 and SV2, a CBC without differential will be performed. The CBC with differential will include: Hb, hematocrit, RBCs, mean corpuscular volume (MCV), mean corpuscular hemoglobin (MCH), mean corpuscular hemoglobin concentration (MCHC), red cell distribution width (RDW), white blood cell (WBC) count with differential (neutrophils, lymphocytes, monocytes, eosinophils, basophils), and platelets.

Hemoglobin assessed by central laboratory CBC will be used for evaluations of efficacy and safety. Hemoglobin levels assessed by HemoCue should be used for dose adjustments, as described in [Section 8.4.4, Dosing and Dose Adjustment Guidelines](#). If the Investigator has an immediate clinical concern about a subject's HemoCue value, the Investigator may use clinical judgement and repeat the HemoCue Hb, use local lab values, or wait for central lab results. The test method utilized to inform the treatment decision must be recorded in the source.

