For eligibility purposes, one retest for Hb may be performed during the screening window. The average of 2 Hb values measured by the central laboratory during Screening (SV1, SV2, or retest) must be between 8.0 and 11.0 g/dL (inclusive). Refer to [Section 7.4.1, Retesting](#) and [Section 7.4.2, Rescreening](#) for further details regarding repeating laboratory measurements during the Screening period.

- Point of Care Hb: Using HemoCue, Hb will be monitored throughout the study to determine if the dose of study medication (vadadustat or darbepoetin alfa) will be adjusted, interrupted, or maintained as described in Section 8.4.4, Dosing and Dose Adjustment Guidelines.
- Reticulocyte Count: An automated reticulocyte count (both absolute and percent) will be performed at Baseline and at Weeks 4, 12, 28, and 52.
- Coagulation Tests: Blood samples will be drawn at Baseline to assess the prothrombin time (PT), partial thromboplastin time (PTT), and international normalized ratio (INR).
- Folate and Vitamin B₁₂: A blood sample will be drawn at SV1 to assess the folate and Vitamin B₁₂ levels.
- C-reactive Protein (CRP): A blood sample for CRP will be collected at Baseline, Weeks 28, 52, 104, 156, and EOT.
- Serum Chemistry: Blood samples to assess serum chemistry will be collected at SV1, Baseline, and twice annually at Weeks 28, 52, 76, 104, 128, 156, 180, 208, and EOT. The serum chemistry will include the following assays: sodium, potassium, bicarbonate, chloride, calcium, magnesium, phosphorus, glucose, creatinine, blood urea nitrogen (BUN)/urea, creatine phosphokinase (CPK), uric acid, albumin, and total protein.

- Liver Function Tests: Blood samples to assess liver function will be collected at SV1, Baseline, Weeks 4, 8, 12, 16, 20, 24, 28, 36, 44, 52, 64, 76, 88, 104, 116, 128, 140, 156, 168, 180, 192, 208, and EOT. Liver function tests will include: total bilirubin, alkaline phosphatase, ALT/SGPT, AST/SGOT, and lactate dehydrogenase (LDH).
- Iron Indices: Blood samples to assess the iron indices will be collected at SV1, Baseline, Weeks 4, 8, 12, 20, 28, 36, 44, 52, 64, 76, 88, 104, 116, 128, 140, 156, 168, 180, 192, 208, and EOT. Assessments will include the following indices: ferritin, iron, TIBC, and TSAT.

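### The 48–72 h repeat liver panel in Section 10.1.1 names neither INR nor a differential, so study drug can be resumed with the INR stopping criterion of Section 9.4 unmeasured

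*Protocol*

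**What the plan says.** All references are to the current protocol, Version 7.0.

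- **Stopping rules.** Section 9.4, Table 2, makes discontinuation mandatory if any one of its rows is met. One row is "ALT or AST >3x ULN and INR >1.5". The last row is "ALT or AST >3x ULN with symptoms including e.g., fatigue, nausea, vomiting, right upper quadrant pain, fever, rash or eosinophilia". The synopsis closes the bracket around the symptoms before the final item, "right upper quadrant pain, fever, rash) or eosinophilia", so there eosinophilia stands as a trigger of its own. On either reading, an eosinophil count is needed to judge it.
- **Repeat testing.** Section 10.1.1 covers a new ALT or AST above 3x ULN without bilirubin above 2x ULN. Drug is held, then: "Repeat testing of ALT, AST, ALP, and total bilirubin, should be completed within 48 to 72 hours". The stated aim is to confirm the finding and see its trend.
- **Resumption.** "Study medication should not be resumed until monitoring indicates abnormalities have resolved, are stable, or are not rapidly increasing".
- **Routine schedule.** For coagulation, Section 9.2.2 says: "Blood samples will be drawn at Baseline to assess the prothrombin time (PT), partial thromboplastin time (PTT), and international normalized ratio (INR"). A CBC with differential is done at Baseline and then "twice annually at Weeks 28, 52, 76, 104, 128, 156, 180, 208". The routine liver panel contains bilirubin, alkaline phosphatase, ALT, AST and LDH.
- **Reporting.** Section 10.1.1 requires the elevation to go to the sponsor's "Medical Monitor or CRO designee within 24 hours of awareness as an SAE".

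**The concern.** A mandatory stopping rule works only if its inputs are measured when the decision is taken. Section 10.1.1 is the only text that tells a site what to test after a new ALT/AST elevation and when drug may be restarted. It names four analytes, and its restart condition refers only to how the abnormalities behave over time. Two results on which Section 9.4 turns, INR and eosinophils, are not requested there, and the routine schedule does not reliably supply them.

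At stake is re-exposure of a subject whom the sponsor's own rule might have required to be stopped permanently. According to Appendix E, Amendment 6 added Section 9.4 in response to regulatory guidance on drug-induced liver injury. The same amendment touched the repeat-testing text but left its analyte list as it was. The likeliest explanation, which is an inference, is that the new rule and the existing panel were not reconciled.

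**Working it through.** The plan gives no figure on this point. The check compares two lists and counts visits.

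**Step 1: inputs to Table 2 against what is measured.**

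| Laboratory input to Table 2 | In the 48–72 h repeat? | Scheduled at numbered post-Baseline liver-test visits |
|---|---|---|
| ALT, AST | yes | 22 of 22 |
| Total bilirubin | yes | 22 of 22 |
| INR | no | 0 of 22 |
| Eosinophils | no | 8 of 22 |

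Of five laboratory inputs (ALT, AST, bilirubin, INR, eosinophils), the repeat supplies three. Its fourth analyte, ALP, appears in no Table 2 row.

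**Step 2: the visit counts** (Sections 9.2.2 and 9.3.5 to 9.3.8).

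- Liver tests: every 4 weeks from Week 4 to Week 28 (7 visits), every 8 weeks from there to Week 52 (3), then four visits in each of Years 2, 3 and 4 (12). 7 + 3 + 12 = 22.
- Differential: two visits a year for four years, 2 × 4 = 8, all of them also liver-test visits. Visits without a differential: 22 − 8 = 14.
- INR after Baseline: 0.
- The EOT visit is left out of the count. Subjects are coming off study drug there, so resumption does not arise, and its CBC is without differential in any case.

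**Step 3: follow one subject.** Suppose a Week 16 liver panel shows a new ALT above 3x but not above 5x ULN, bilirubin is not raised, and the subject has no symptoms.

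1. Section 10.1.1 applies and drug is held.
2. The repeat at 48–72 h returns ALT, AST, ALP and bilirubin, all stable.
3. The restart condition is satisfied and drug may be resumed.
4. The INR row has not been assessed, because no INR exists after Baseline. Eosinophilia has not been assessed either, because Week 16 has no differential.

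Move the same subject to Week 28 and an eosinophil count exists from that visit, so only INR is missing. The INR gap applies at all 22 visits; the eosinophil gap applies at 14.

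**Step 4: look for a provision that closes the gap.** Section 9.4 gives thresholds but orders no test. Section 9.3.11 sets the minimum content of an unscheduled visit as the MACE questionnaire and an AE assessment, with anything else left to the Investigator. Section 10.3.3 asks for careful monitoring until an SAE resolves or stabilizes, without naming tests. None of these requires INR or a differential before resumption.

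**The case against.** The strongest reply is that nothing here conflicts. Section 9.4 is mandatory, Sections 7.5.5 and 10.1.1 both point to it, and 10.1.1 does not call its panel exhaustive. The repeat is meant to confirm and follow the enzymes, not to be a full work-up against Table 2, and restart depends on monitoring in general rather than on one draw. Drug is held meanwhile, the event is reported as an SAE within 24 hours, and extra tests are allowed. For INR to be missed in a reported liver SAE, the Investigator and the sponsor's medical oversight would all have to leave it out.

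Much of this stands, and it limits the point:

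- A reader might infer that 10.1.1 permits what 9.4 forbids. It does not: if the INR were known and high, 9.4 would govern. The gap is that nobody is required to obtain it.
- A reader might infer that two whole criteria always go unassessed. Only the INR row is wholly unassessed. In the last row, the symptom part needs no laboratory test, and the eosinophilia part is missing only when the index visit had no differential.
- A reader might turn the three-of-five analyte count into a share of Table 2 rows that the repeat can settle. That does not work: the row on persistence above 5x ULN over 2 weeks uses only ALT and AST, yet a repeat at 48–72 h cannot show persistence over 2 weeks.

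What the reply does not supply is any text making INR or a differential a condition of restarting drug. The safeguards make an omission less likely, but they leave the tests to case-by-case choice.

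**Conclusion.** The point holds as a gap in a safety procedure. A site that follows Section 10.1.1 exactly can resume drug in an asymptomatic subject with the INR criterion of Section 9.4 never assessed, at any of the 22 numbered post-Baseline liver-test visits. At 14 of those 22, eosinophilia is unassessed as well.

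This rests on two assumptions: the subject meets no other Table 2 row, and no one orders the tests at discretion. How often both hold cannot be estimated from the protocol; the number is expected to be small.

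Severity is minor. The primary efficacy analysis, its power and error rate, and the MACE analysis are unaffected. It is still worth correcting, because the rule is mandatory, one of its criteria has no required post-Baseline measurement, and the correction is cheap.

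**What to change.** In Section 10.1.1:

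1. Extend the 48–72 h repeat to ALT, AST, ALP, total bilirubin, INR and a CBC with differential.
2. Allow study medication to be resumed only once those results are available and no Section 9.4 criterion is met, in addition to the present condition on resolution or stability.

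**Cost.** Two edited lines, a laboratory-manual update, and two extra assays at a draw that already takes place, only in subjects with a new ALT or AST above 3x ULN.

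**Side effect.** Some anticoagulated subjects may exceed an INR of 1.5 because of their anticoagulant. They can be enrolled: Section 7.3 excludes DVT or PE only within 12 weeks before randomization, and the Amendment 1 entry in Appendix E says that chronic anticoagulation for an older event does not exclude. The sponsor may, as an option, address this in Section 9.4, for example by judging INR against the Baseline value every subject is scheduled to have. That would bring judgment into a row that is now absolute, and it is a separate choice from closing the gap.

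**What the fix does not do.** It does not settle the 2-week persistence row. A subject with a stable ALT of 6x ULN could still pass the restart condition at 72 h, before that row has had time to be met; there the footnote to Table 2 discouraging re-challenge above 5x ULN is the relevant safeguard.
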